Subjects will receive conservative standard of care treatment plus two ITU treatments (week 0 and week 4) on the affected CET (figure 2) using the ultrasound therapy device. Treatments will be up to 10 minutes in duration. A 2, 4, and 8 week follow up period will be included to monitor the effects of the therapy post treatment. A 12 and 24-26 week telephone assessments for the primary objectives will also be included. Telephone assessments will consist of the subjects answering the survey questions over the phone.

Subject self-assessments will be conducted before the treatment phase and during the follow-up period. Physical exams will be completed by a physician. Physical therapy will be completed by a therapist. ITU treatment and diagnostic ultrasound will be performed by Guided Therapy personnel as shown in the full schedule of events (Appendix 1).

[figure not shown]

Figure 2: Treatment Area

SELECTION OF SUBJECTS**Planned number of subjects**

The study population will consist of up to 25 subjects with unilateral CET tendinosis defined as pain lasting more than 3 months with little or no improvement following conservative standard of care alone.

The selection of suitable subjects will be made according to the inclusion and exclusion criteria described in the following sections.

Inclusion Criteria

1. Subjects who are in general good health and are willing to cooperate and participate by following study requirements for the duration of the study, and to report any adverse symptoms immediately;
2. Subjects who have provided written and verbal informed consent;
3. At time of enrollment subjects are between the ages of 21 and 65 years
4. Subjects literate in English and able to complete all patient self-assessment questionnaires;

5. Subjects is willing to refrain from beginning any additional treatment during the duration of the study;
6. Subjects is willing to refrain from changing physical activity during the duration of the study;
7. Subjects diagnosed with unilateral CET tendinosis defined as pain lasting more than 3 months with little or no improvement following conservative standard of care alone.
8. Subjects with BMI ≤ 35 or at the discretion of the PI.
9. Subjects must be able to sit in a chair with their arm on an appropriate table for the treatment and diagnostic ultrasound imaging.
10. Subject must be able and willing to complete the at home therapy regimen.

Exclusion Criteria

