Diagnostic Ultrasound Imaging will be performed by a trained Sonographer using the Spark® Imaging System, manufactured by Ardent Sound, Inc., Mesa, AZ USA (Appendix 7-B)

Subjects will be imaged seated with their arm resting on a structure that is comfortable for the subject and sonographer.

PolySonic® or AquaSonic® Gel will be applied by the sonographer as required to maintain adequate acoustic coupling. (Appendix 7-C)

1

[figure not shown]
Images will be preserved with the following notations:

- Protocol ID
- Right vs. Left CET Tendon
- Treated vs. Untreated

Long Axis and Short Axis (if necessary) images will be stored at the Sonographer's discretion, to demonstrate and track the applicable anatomy/pathology in the peri-CET area.

Sonographer will also measure the thickness of the CET tendon in each applicable image.

Sonographer will scan the contralateral CET tendon in the same manner noting the change in the tendon (Right v. Left) and (Treated v. Untreated).

Common Extensor Tendon
Figure 4: representative long axis ultrasound images

Outcome measures

Subjects will complete subject reported outcome measures at 0, 2, 4, 8, 12, and 24 weeks and will undergo a focused physical examination and diagnostic ultrasound at 0, 2, 4, and 8 weeks. Adverse events will be recorded at each visit. Treatment tolerability will be assessed immediately after each treatment using the Visual Analog Scale for Pain (VAS) or Universal Pain Assessment Tool (Appendix 3-B). The VAS will be used for 2 different assessments: 1. Pain related to physical activity of the symptomatic arm before treatments and at follow-up visits and phone surveys. 2. Pain tolerance of the therapy treatment. Each of these assessments will be documented and evaluated separately.

Aim 1: reported outcomes

The principal aim of this study is to assess the efficacy of treatment and time course of response to treatment using validated subject reported outcome measures assessing pain, function and level of activity. Subjects will complete validated subject reported outcome questionnaires assessing pain, function and level of activity prior to initiating treatment and at

0, 2, 4, 8, 12, and 24 weeks after starting treatment (Appendix 2 and 3A).

Clinical Pain and Treatment Tolerance will be assessed using the Visual Analog Scale for Pain (VAS) or Universal Pain Assessment Tool (Appendix 3-B).

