TITLE: STUDY TO EVALUATE THE SAFETY, EFFICACY AND TOLERANCE OF INTENSE THERAPEUTIC ULTRASOUND (ITU) FOR THE TREATMENT OF LATERAL EPICONDYLITIS

PROTOCOL NO. and WIRB NO: 20150654

DATE: March 2, 2015

Principal Investigator: [name]

The More Foundation
[name]
[name]
[name]

Sponsor: Guided Therapy Systems
[name]
[name]

Statistical Analysis Plan:

Statistical Methods

Pain Reduction:

Pain level for subjects at the region of interest was self-reported at pre-treatment, used as baseline, and again at each follow-up at 4, 8, 12, and 26 weeks following initial treatment. The pain scale subjects used to identify their level of pain was a 10-point pain scale, where 0 = no pain, 1 = slight pain, through 10 which equates to the patients' worst imaginable pain. The goal for all subjects was to reduce pain by at least 25%. For patients reporting an initial (baseline) score ranging 6-10, this reflects a VAS pain score reduction \geq a 2 point drop; for initial scores ranging 2-5, this reflects a VAS pain score reduction \geq a 1 point drop. Pain scores reported at follow-up timepoints were compared to baseline score for each subject to determine if the goal was met by dividing the difference in the follow-up and baseline pain score by the baseline pain score. The percentage of subjects that met the pain reduction goal was calculated at each timepoint for both groups by dividing the number of subjects that achieved the pain reduction goal at that timepoint by the total number of patients that gave a pain score for that timepoint.

Patient Rated Tennis Elbow Evaluation Score Reduction:

In addition to the 10-point VAS pain scale, patients self-reported answers to questions from the Patient Rated Tennis Elbow Evaluation (PRTEE) questionnaire, which has been standardized for use in research studies to evaluate patient's level of pain and function ^[10]. Scores range from 0-100, with 0 indicating no pain and 100 indicating the worst pain imaginable in a variety of daily activities. Self-reported scores were taken at baseline and each follow-up timepoint. The average score for each timepoint were calculated, and follow-up averages were compared to baseline to calculate the percentage reduction in score.

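### The PRTEE reduction compares visit averages that are not tied to the same subjects and has no interval, and the pain-responder rate counts only those who answered

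*SAP*

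**What the plan says.** The protocol (Assessment of Efficacy) names several primary endpoints, with the PRTEE total score first. The SAP paragraph on PRTEE averages the scores at each timepoint, and then "follow-up averages were compared to baseline to calculate the percentage reduction in score". It does not say whether the baseline average is limited to subjects who also have the follow-up score. It gives no SD, interval or test.

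For pain, the SAP does work within subjects: "Pain scores reported at follow-up timepoints were compared to baseline score for each subject". The number reaching the 25% goal is then divided "by the total number of patients that gave a pain score for that timepoint". That is a stated rule: a subject without a score leaves the denominator. No interval is given here either.

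The protocol does not fill the gap:
- The statistical analysis text under Aim 1 has PRTEE and VAS looked at before and after treatment, with checks of normality and variance.
- Aim 2 names paired t tests at P<0.05, but only for tendon thickness.
- Statistical Methods adds descriptive statistics for comparison with the literature.
- The Appendix 2 scoring instructions deal with blank items on a returned form, not with a form that was never completed.
- Withdrawal of Subjects lets subjects leave at any time. Those who leave may be asked back for some closing procedures.
- Sample Size Calculation enrols at most 25 and expects at least 25 to complete.

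**The concern.** The Study Outline gives ITU to every subject: "Subjects will receive conservative standard of care treatment plus two ITU treatments (week 0 and week 4) on the affected CET". Change from baseline therefore carries the efficacy evidence. A percentage formed from two averages over different people mixes real change with a change in who is being averaged. A responder rate among those who answered says nothing about those who did not.

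Loss related to outcome is possible under the protocol's own rules. Subjects agree not to begin other treatment (Inclusion Criteria, item 5), and non-compliance can lead to removal (Withdrawal of Subjects). Under Quality Standards the sponsor, which also performs the analysis, may leave out data from major deviations.

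Even with full retention, a PRTEE percentage without an interval cannot be judged against chance. Yet Statistical Methods presents 25 subjects as enough to show significance with 80% power.

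**Working it through.** **The plan's own figure.** Statistical Methods gives 25 per-protocol subjects, two-sided alpha 0.05 and 80% power. It states no effect, SD or test, so 25 cannot be rebuilt. Solved backwards for a paired t test, it corresponds to a standardised effect of 0.584 (normal approximation: (1.960 + 0.842)/√25 = 0.560). At 0.584, power is 76% with 23 subjects and 70% with 20. There is no allowance for loss.

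The documents give no PRTEE mean, SD or dropout rate, so every input below other than n = 25 and the visit weeks is an assumption.

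**1. The missing interval, nobody lost.** Half-width = t(0.975; 24 df) × SD/√25 = 2.064 × SD/5. SD of change 15, 20 and 25 gives 6.2, 8.3 and 10.3 points.

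**2. PRTEE averages when subjects are lost and nobody changes.** Let M be the overall baseline mean, k the number missing, and g the missing subjects' baseline mean minus the completers'. The follow-up average is then M − g × k/25, and the apparent reduction is 100 × g × k/(25 × M) percent.
- M = 50, k = 5: g = +10 gives 48.0 (4% reduction) and +20 gives 46.0 (8%). g = −10 gives 52.0 and −20 gives 54.0 (4% and 8% increase).
- M = 50, g = 10 to 20: k = 2 gives 1.6 to 3.2%, k = 1 gives 0.8 to 1.6%, k = 0 gives none.
- k = 5, g = 10 to 20: M = 40 gives 5 to 10%, M = 60 gives 3.3 to 6.7%.

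**3. Pain responders (exact 95% CI).**
- 5 missing: 12/20 = 60% (36 to 81%) as the SAP counts. Over all 25 the rate lies between 12/25 = 48% (28 to 69%) and 17/25 = 68% (46 to 85%).
- 2 missing: 14/23 = 61% (39 to 80%). Over all 25 it lies between 14/25 = 56% (35 to 76%) and 16/25 = 64% (43 to 82%).

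The observed-case rate can therefore be too high or too low, but it cannot create responders where there are none.

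**4. Is comparing the same subjects enough?** Simulation: 25 subjects at weeks 0, 2, 4, 8, 12 and 24, mean 50, SD 18, no true change, five lost after week 4, five correlation patterns. There were 6,000 runs per cell (20,000 for the paired entry in the second row). The mixed-model column rests on one set of runs. Entries are errors in the week-8 change, in points; negative means false improvement.

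| Who is lost | SAP averages | Paired change | Random intercept plus serial term |
|---|---|---|---|
| Nobody | within 0.1 | within 0.1 | within 0.1 |
| Five highest week-4 scores | −3.1 to −4.9 | 0.0 in four patterns, size about 1.3 in the fifth | within 0.8 |
| Five largest worsenings by week 4 | 0.0 to −2.2 | −2.3 to −5.2 | +0.1 to −0.9 |
| Five highest unseen week-8 scores | about −6 | −1.8 to −4.1 | −2.0 to −4.0 |

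Losing the five lowest week-4 scores instead moves the SAP figure by +3.0 to +4.9. Paired change removes most of the error in the second row, does as well as the model in the last, and is worse than the SAP figure in the third. No method is safe in the last row.

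**5. What a shift analysis does.** Making 5 missing subjects 10 or 20 points worse moves the mean by 10 × 5/25 = 2.0 or 20 × 5/25 = 4.0 points.

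**The case against.** There may be no loss. Exclusion criterion 13 screens out subjects unavailable for on-site visits, and the later assessments are by phone or online. This stands as far as it goes: with complete data neither point estimate is distorted. It does not supply the interval.

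The study is small and Statistical Methods promises descriptive statistics. But the same section claims significance and power, and no PRTEE test or interval exists to deliver either.

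A plain paired change might do. That partly stands, as the table shows, so the exact covariance form of a model is a matter of choice. Paired change should not stand alone, because it fails when subjects leave after worsening.

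A reader might also infer more than the documents support:
- *That the SAP has no missed-visit rule at all.* For pain it has one, and its denominator is stated. Only PRTEE lacks a rule.
- *That the denominator is undefined because the percentage* "was calculated at each timepoint for both groups by dividing the number of subjects". The same paragraph has just divided patients into baseline scores 6-10 and 2-5, and the phrase may mean those bands.
- *That the visit lists undo the analysis.* The SAP's pain paragraph has scores "again at each follow-up at 4, 8, 12, and 26 weeks following initial treatment", while the protocol says "Subjects will complete subject reported outcome measures at 0, 2, 4, 8, 12, and 24 weeks" and elsewhere "A 12 and 24-26 week telephone assessments for the primary objectives will also be included". The PRTEE paragraph refers to every follow-up without listing weeks, and the protocol's own range reaches week 26. Both wordings need reconciling, as separate points.
- *That the sponsor may drop data without criteria.* Quality Standards defines a major deviation by its effect on study integrity or subject safety, and requires submission to the sponsor and the IRB. What remains is that the exclusion decision is the sponsor's and its timing is not stated.

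**Conclusion.** The point holds. The SAP's PRTEE comparison is not tied to the same subjects and has no interval, test or missed-visit rule. The pain rate is an available-case rate without an interval. No protocol text repairs this.

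The missing interval matters whatever the retention: about ±6 to ±10 points at n = 25 if the SD of change is 15 to 25. The distortion arises only with loss. Under the assumed inputs with five missing, it is 4 to 8% of the PRTEE mean in either direction, and the pain rate reads 60% against 48% if the missing are non-responders.

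The documents do not support a claim that the plan favours ITU, or that the error has a known size, because they give no dropout figures. This is a change that should be made because it is cheap and concerns a primary endpoint. It is not proof that any result is wrong.

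**What to change.** 1. **PRTEE.** Report within-subject change from baseline with a 95% CI and the number observed at each visit, over all subjects who received the first ITU treatment. Use a simple pre-specified repeated-measures model on all observed scores, with baseline as a visit, and put paired change in subjects with both scores beside it. State that neither removes bias when loss depends on unseen scores, and that paired change can be more biased than the SAP figure when subjects leave because they worsened. Add one sensitivity analysis that makes missing subjects worse by an amount fixed in advance. Keep the percentage reduction as descriptive.
2. **Pain.** Report the responder rate over all treated subjects with a non-zero baseline, missing counted as non-responder, with an exact 95% CI, beside the observed-case rate.
3. **Deviations.** Keep these subjects' data in the primary analysis and exclude them only in a sensitivity analysis.

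The SAP is written in the past tense. If outcomes had already been seen, these analyses must be labelled post hoc.

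The cost is SAP and protocol text and a short program, with no new data. The downside is that the missing-as-non-responder rate is equal to or lower than the observed-case rate and may understate benefit.
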